2.1.4 Safety Objectives (Parts A and B)

The safety objectives of this study are:

- 1. To evaluate the safety and tolerability of tozadenant in levodopa-treated PD patients with end-of-dose "wearing-off", based on assessment of AEs, vital signs, electrocardiograms (ECGs), physical and neurological exams, and clinical laboratory tests.
- 2. To evaluate the effects of tozadenant on the occurrence of daytime drowsiness (including episodes of sudden onset of sleep), impulsive behavior, and suicidality.

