2.2.6 Safety Endpoints

The safety and tolerability of tozadenant will be evaluated in this study using the following measures:

- 1. TEAEs.
- 2. Physical and neurological examination.
- 3. Supine and standing pulse and BP.
- 4. Standard 12-lead ECG: RR, PR, QRS, QT and QTcF.

- 5. Laboratory parameters: hematology, chemistry, thyroid function (thyroid stimulating hormone [TSH], free T3, and free T4), and urinalysis.
- 6. Columbia-Suicide Severity Rating Scale (C-SSRS).
- 7. Daytime sleepiness as measured by the Epworth Sleepiness Scale (ESS), including assessment of episodes of sudden onset of sleep.
- 8. Modified Minnesota Impulse Disorders Interview (mMIDI).

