draw (hematology only) at Weeks 28, 32, 34, 40, 44 and 68. The Safety Follow-Up Visit will occur 28 ± 3 days after the patient's last open-label dose of tozadenant. Patients who received tozadenant during Part A will continue on open-label tozadenant and those who received placebo will initiate open-label tozadenant. Neither the patient nor the investigator will be unblinded to the treatment received during Part A unless required for safety purposes as determined by the investigator and agreed to by the Sponsor. Upon starting Part B, patients will receive open-label tozadenant at a dose of 120 mg BID. Adjustments to the open-label tozadenant dose are allowed starting at Week 26 and at subsequent visits. Doses of 60 or 120 mg BID are permitted; the investigator may adjust a patient's dose to either level as clinically indicated. Because the information entered in the Interactive Response System (IXRS) will be used to manage the tozadenant inventory at each study site, timely entries into the IXRS will be important.

During Part B, patients' concomitant anti-PD medications may be adjusted as needed under the investigator's supervision (see **Section 5.9.1**). The optimal dose of open-label tozadenant for each patient will be defined following discussion between the patient and the investigator, taking into account the potential for improvement of disease symptoms and the tolerability profile.

During Part B, Unscheduled Visits can be arranged as considered necessary by the investigator (see Section 6.2.34). In the event of Early Termination during Part B, patients will be asked to complete an Early Termination Visit as soon as possible (see Section 6.2.33) and then return 28 ± 3 days after their last dose of IMP for a Post-Early Termination Safety Follow-Up Visit (Section 6.2.35). Safety data from Part B will be provided to the DSMB, at a frequency specified by its charter, for ongoing monitoring of safety and detection of any trends.

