 - a. Perform full UPDRS Parts I, II, III (motor) and IV, approximately 1 to 3 hours after the patient has taken a scheduled dose of levodopa (preferably their morning dose of levodopa). UPDRS in the ON state will be measured at a time representative of the ON state in that patient, not in "best" ON.
 - b. Administer the following assessments:
 - CGI-I.
 - CGI-S.
 - SCOPA-cog.
 - c. Have the patient complete the following self-assessment questionnaires:
 - PGI-I.

- ESS.
- PDQ-39.
- EQ-5D-5L.
- TSQM-9.
- 10. Administer the following assessments (may be done anytime during visit):
 - mMIDI. (Note: After Baseline, if patient has one or more positive modules on the mMIDI, their continued participation in the study should be discussed with the Medical Monitor.)
 - C-SSRS.
 - Assessment for episodes of sudden onset of sleep.
 - Fall questionnaire.
 - Healthcare Resource Utilization
- 11. Obtain second PK blood sample for plasma tozadenant concentration, approximately 45 minutes or longer after the first PK sample collection, and record the date and time of the second PK collection.
 - For patients concomitantly taking pramipexole, plasma will also be analyzed for pramipexole plasma concentration using the same PK blood sample as drawn for tozadenant PK. Record the patient-reported date and approximate time when the patient took the previous dose of pramipexole prior to sampling.

- 12. Perform physical and neurological examination, and assess any changes from Baseline for clinical significance.
- 13. Collect the IMP kit (including all used, unused and partially used blister cards) dispensed at the Week 18 visit.
- 14. Record the date and approximate time when the patient took the last dose of double-blind IMP
- 15. Assess and document IMP accountability and compliance (document any missed dose(s), lost tablets and number of tablets taken).
 - a. Review and reconcile any discrepancies with the patient.
- 16. Dispense open-label IMP (bottles) according to IXRS.
 - a. Record the date IMP was dispensed on front of bottle(s) and in IMP dispensing records.
- 17. Review the dosing instructions for open-label IMP with the patient, answer any questions, and remind the patient to return unopened and opened IMP bottles at the next visit.

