- a. Patient will begin dosing in the open-label phase (Part B) at the 120 mg dose level (i.e., two [2] tablets of open-label tozadenant 60 mg taken by mouth BID, in the morning and evening preferably at the same time each day, for a total of four (4) tablets per day).
- b. Remind the patient that the first dose of open-label IMP will be taken at home in the evening.
- c. Ask the patient to refrain from taking their morning dose on the day of their next visit (Week 26).
- d. Document patient understood dosing instructions.
- 18. Schedule the Week 26 Visit in the morning before 10 AM. If needed, use the visit window in relation to the date of the Week 24 visit (when Part B began for a given patient).

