6.2.35 Post-Early Termination Safety Follow-Up Visit

After Early Termination, the patient will also be asked to return for a Safety Follow-Up Visit to be scheduled 28 days after the last dose of IMP. If an Early Termination Visit took place 28 or more days after the last dose of IMP, this visit will not be conducted.

Note: Confirm the arrangement for laboratory sample pick-up on the day of the visit with the courier (see Central Laboratory Procedures Manual).

- 1. Assess AEs by asking open-ended queries and record the assessments.
- 2. Record concomitant medication use; assess and record any changes to anti-PD medication dose or regimen.
- 3. Obtain and record BP and pulse measurements after at least 5 minutes supine rest and again after standing for approximately 1 and 3 minutes.
- 4. Obtain 12-lead ECG and ensure the ECG is collected at a time when the patient is not experiencing dyskinesia that would interfere with an adequate recording. Assess any changes from Baseline for clinical significance.
 - Part B only: Obtain weight.
- 5. Have the patient complete the following self-assessment questionnaire:
 - Parts A and B: ESS.
- 6. Administer the following assessments (may be done anytime during visit):
 - Parts A and B: mMIDI.
 - Parts A and B: C-SSRS.
 - Part A only: Assessment for episodes of sudden onset of sleep.
- 7. Obtain samples for the following laboratory tests and record the date and time of collection:
 - a. Hematology and chemistry (inclusive of liver function tests).
 - b. TSH, free T3, and free T4.
 - c. Urine sample for urinalysis.
 - d. Verify method of contraception has not changed since the previous visit. For females of childbearing potential: urine pregnancy test.

8. Perform physical and neurological examination, and assess any changes from Baseline for clinical significance.

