9.5.5 Assessment for Episodes of Sudden Onset of Sleep

To assess the potential development of episodes of sudden onset of sleep, patients will be asked if they experienced any abrupt episodes of unplanned sleep during or while engaged in some activity where they are not expected to occur (e.g., eating/drinking, speaking, or driving), which may or may not have been preceded by somnolence or sedation. Any positive response should be further evaluated to determine whether the patient's continued participation in the study puts them at risk and whether they should be discontinued from the study (see **Appendix 15.6**).

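### The safety objective for Parts A and B includes sudden onset of sleep, but Part B has no structured assessment of it, so that component cannot be evaluated systematically after Week 24

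*Protocol*

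**What the plan says.** Safety objective 2 in Protocol 2.1.4 reads: "To evaluate the effects of tozadenant on the occurrence of daytime drowsiness (including episodes of sudden onset of sleep), impulsive behavior, and suicidality". The section heading assigns it to both parts of the study, and the synopsis does the same. Endpoint 7 in 2.2.6 is "Daytime sleepiness as measured by the Epworth Sleepiness Scale (ESS), including assessment of episodes of sudden onset of sleep". Neither that entry nor the matching safety variable in 11.2.2 is limited to Part A.

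Table 1 schedules the dedicated question at Baseline, Weeks 2, 6, 12, 18 and 24, Part A Early Termination and the follow-up visit after it. The last scheduled use for a patient who continues is Week 24 (6.2.18: "Assessment for episodes of sudden onset of sleep"). The same visit starts open-label treatment: "Remind the patient that the first dose of open-label IMP will be taken at home in the evening".

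Table 2 has no row for the question. It is missing from the Part B visit lists (6.2.19 to 6.2.31) and from Part B Early Termination (6.2.33). For the visit after Early Termination, 6.2.35 item 6 says: "Part A only: Assessment for episodes of sudden onset of sleep".

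On entering Part B, "those who received placebo will initiate open-label tozadenant" (3.1), and every patient starts at 120 mg BID. Section 9.5.5 attaches an action to the question: "Any positive response should be further evaluated to determine whether the patient's continued participation in the study puts them at risk".

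**The concern.** A named component of a stated safety objective loses its only dedicated instrument at the moment treatment changes for most patients. Ascertainment and exposure change together at Week 24, so a low Part B count could mean few episodes or simply that nobody asked in the same way. The count could not be set beside Part A. The individual evaluation that 9.5.5 ties to a positive answer would also depend on a patient raising the matter unprompted or on a less specific item.

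**Working it through.** **Plan's own figure.** Sections 3.1.2 and 11.10 give 450 randomized, 150 per arm, with 80% expected to continue. 450 × 0.80 = 360, as stated.

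**Patients whose tozadenant exposure starts or doubles at Week 24.** These are the former placebo and 60 mg BID arms. The documents give only an overall continuation rate, so equal continuation by arm is an assumption.

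- Equal 80%: 2 × 150 × 0.80 = 240 of 360 (67%), of whom 150 × 0.80 = 120 are former placebo patients.
- If the total stays at 360 but the 120 mg BID arm continues at rate r, the number is 360 − 150r: 255 at r = 0.70, 240 at r = 0.80, 225 at r = 0.90.

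**Objective 2 set against the Part B schedule (Table 2 and 6.2.19 to 6.2.33).**

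| Component | Part B assessment | When |
|---|---|---|
| Sudden onset of sleep | none dedicated | never scheduled |
| General daytime drowsiness | Epworth scale (ESS) | Weeks 36, 48, 76, 80, Early Termination |
| Impulsive behavior | mMIDI | Weeks 30, 36, 48, 60, 76, 80, Early Termination |
| Suicidality | C-SSRS | every full visit from Week 26, Early Termination |

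**Can the other Part B sources stand in for the question?**

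- Open-ended adverse event query, at every full visit: 9.1.2 requires it to be non-leading, so it does not ask about these episodes.
- UPDRS item 41, at Weeks 26, 30, 36, 48, 60 and 76: one yes/no answer on any sleep disturbance, combining insomnia with hypersomnolence, over the past week.
- PDQ-39 item 30, on falling asleep unexpectedly: only at Week 76 and Early Termination, and covering the last month.
- ESS: rates the likelihood of dozing in eight situations. It does not record discrete episodes.

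None asks whether an episode has occurred since the last visit, and none separates episodes with and without prior sleepiness, as Appendix 15.6 does.

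**ESS timing.** The first scheduled Part B ESS comes 36 − 24 = 12 weeks after the switch, 81 to 87 days with the ±3-day window, or 12/52 = 23% of the open-label period. In Part A it is first repeated at Week 2.

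**Would adding the question restore comparability?** Weeks 26, 30 and 36 fall 2, 6 and 12 weeks after the switch, which matches Weeks 2, 6 and 12 of Part A. The recall intervals also match (2, 4 and 6 weeks). Later intervals are longer in Part B: 12 weeks to Week 48, 12 to Week 60 and 16 to Week 76, against 6 weeks in late Part A.

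**The case against.** The best defence is that Part B was deliberately given a lighter schedule. Section 6.2.35 separates items for both parts from those for Part A, which suggests a choice rather than an oversight. The placebo-controlled comparison exists only in Part A. Episodes a patient reports are still recorded as adverse events, 9.1.2 has investigators review the self-assessments, and 4.3.1 item 3 requires discussion with the Medical Monitor when an adverse event puts a patient at additional risk. UPDRS item 41 brings a directed question on hypersomnolence only 2 weeks after the switch, and patients who stop early in Part B get an ESS and a PDQ-39.

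Much of this stands, and it rules out several stronger readings:

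- A reader might infer that objective 2 as a whole cannot be answered in Part B. The documents do not support this: drowsiness, impulsive behavior and suicidality keep their instruments.
- A reader might infer that Part B holds no information on these episodes, or that 9.5.5 could never be invoked. Unstructured reports remain possible; what is missing is a scheduled trigger and systematic counting.
- A reader might compute planned tozadenant exposure as 300 × 24 = 7,200 patient-weeks in Part A and 360 × 52 = 18,720 in Part B, and conclude that 18,720/25,920 = 72% goes unquestioned. That share assumes full exposure, concerns one form only, and ignores the other sources above.
- A reader might treat the 12-week wait for the ESS as an error. No section promises an earlier one, and Week 24 supplies a value before the switch.
- Section 11.5.1 summarizes data at the time points measured, so it promises no Part B time point. The SAP covers Part A only, so its silence on Part B is not a fault.

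The defence does not remove the mismatch. If the reduction was deliberate, the objective and endpoint should say so.

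**Conclusion.** The point holds for one component. The protocol sets an objective on sudden onset of sleep for both parts, but schedules no structured assessment of it in Part B, where about 240 of 360 patients start tozadenant or move to the higher dose. That number rests on equal 80% continuation by arm; it is 225 to 255 if continuation in the 120 mg BID arm is between 90% and 70% and the total stays at 360. The remaining sources can pick up individual cases but cannot support a Part B frequency comparable with Part A. The mismatch itself follows from the visit schedule and needs no numerical assumption. It does not affect the Part A safety comparison or any efficacy analysis.

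**What to change.** Reconcile the objective with the schedule in one of two ways.

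1. Add the existing Appendix 15.6 question, in its form for visits after Baseline, to Table 2 and the visit lists at Weeks 26, 30, 36, 48, 60, 76 and 80 and at Part B Early Termination, and remove the Part A restriction in 6.2.35 item 6. The Part B analysis plan should then allow for the longer recall intervals after Week 36.
2. Otherwise, restrict the sudden-onset-of-sleep component of objective 2 (2.1.4 and the synopsis) and of endpoint 7 (2.2.6, 11.2.2) to Part A, and draw no Part B conclusion on it.

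The first costs a protocol amendment, reuse of a form that already exists, and one check-box question at visits that already take place. The second costs wording only, but gives up the Part B evidence. An ESS at Weeks 26 and 30 would be a useful option for describing early drowsiness after the switch; it is an addition, not the correction of an error.

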2.2 Efficacy Endpoints

2.2.1 Primary Efficacy Endpoint (Part A)

The primary efficacy endpoint will be the change from Baseline to Week 24 in the number of hours per day spent in the OFF state, as assessed by patient-completed PD diaries and averaged over 3 consecutive days.

2.2.2 Key Secondary Efficacy Endpoints (Part A)

The key secondary efficacy endpoints, to be analyzed according to a prespecified hierarchy of hypotheses, include:

- 1. Change from Baseline to Week 24 in the number of hours per day spent in good ON time, defined as the sum of ON time without dyskinesia and ON time with non-troublesome dyskinesia.
- 2. Change from Baseline to Week 24 on UPDRS Parts II (ADL subscale) + III (motor subscale) total scores.

2.2.3 Other Secondary Efficacy Endpoints (Part A)

The other secondary efficacy endpoints include the change from Baseline to Week 24 (where applicable), for the following:

1. CGI-I at Week 24.

- 2. PGI-I at Week 24.
- 3. UPDRS Part III (motor subscale) score in the ON state.
- 4. Investigator global impressions of severity of illness (CGI-S).
- 5. UPDRS Part II (ADL subscale) score.
- 6. Number of hours per day spent in the ON state (without dyskinesia, with non-troublesome dyskinesia, or with troublesome dyskinesia).
- 7. Number of hours per day spent in the ON state without dyskinesia.
- 8. Number of hours per day spent in the ON state with any dyskinesia (troublesome or non-troublesome).
- 9. Number of hours per day spent in the ON state with non-troublesome dyskinesia.
- 10. PDQ-39 (total score and individual domain scores).
- 11. UPDRS Part IV.
- 12. UPDRS Part I.

2.2.4 Exploratory Endpoints (Part A)

The exploratory endpoints in Part A include the change from Baseline to Week 24 (where applicable), for the following:

- 1. Number of hours per day spent in the asleep state.
- 2. Dyskinesia as measured by questions 32, 33 and 34 of UPDRS Part IV.
- 3. Falls as measured by question 13 on UPDRS Part II.
- 4. Responder analysis of number (%) of patients with ≥ 1.0 h improvement in OFF time (evaluated at Week 24).
- 5. Responder analysis of number (%) of patients with \geq 2.0 h improvement in OFF time (evaluated at Week 24).
- 6. Percent change in total levodopa equivalent dose.
- 7. Percent change in the number of hours per day spent in OFF state.
- 8. Percent change in the number of hours per day spent in ON state without troublesome dyskinesia.
- 9. Percent change in the number of hours per day spent in ON state with troublesome dyskinesia.
- 10. Scales for Outcomes in Parkinson's Disease–cognition (SCOPA-cog) score.
- 11. Fall questionnaire score.

- 12. Number of hours per day spent in the OFF state in the sub-population of subjects taking levodopa and only one additional concomitant anti-PD medication.
- 13. Number of hours per day spent in the OFF state in the sub-population of subjects taking levodopa and two additional concomitant anti-PD medications.
- 14. Number of hours per day spent in the OFF state in the sub-population of subjects taking levodopa and three additional concomitant anti-PD medications.
- 15. EuroQol 5D-5L Health Questionnaire (EQ-5D-5L).
- 16. Treatment Satisfaction Questionnaire for Medication (TSQM-9) (evaluated at Weeks 6 and 24).

2.2.5 Exploratory Endpoints (Part B)

The exploratory endpoints in Part B include the following:

- 1. Change from Baseline in UPDRS Part II (ADL subscale) + Part III (motor subscale) total score.
- 2. Change from Baseline in UPDRS Part II (ADL subscale) score.
- 3. Change from Baseline in UPDRS Part III (motor subscale) score in the ON state.
- 4. Change from Baseline in UPDRS Part I total score.
- 5. Change from Baseline in UPDRS Part IV total score.
- 6. Change from Baseline in dyskinesia as measured by questions 32, 33 and 34 of UPDRS Part IV.
- 7. Change from Baseline in SCOPA-cog score.
- 8. Change from Baseline in Fall questionnaire score.
- 9. Percent change from Baseline to the end of open-label treatment in total levodopa equivalent dose.
- 10. Exploratory endpoints to evaluate potential disease modification (see Section 11.4.6).
- 11. EQ-5D-5L.
- 12. TSQM-9 (evaluated at Week 76).

2.2.6 Safety Endpoints

The safety and tolerability of tozadenant will be evaluated in this study using the following measures:

- 1. TEAEs.
- 2. Physical and neurological examination.
- 3. Supine and standing pulse and BP.
- 4. Standard 12-lead ECG: RR, PR, QRS, QT and QTcF.

- 5. Laboratory parameters: hematology, chemistry, thyroid function (thyroid stimulating hormone [TSH], free T3, and free T4), and urinalysis.
- 6. Columbia-Suicide Severity Rating Scale (C-SSRS).
- 7. Daytime sleepiness as measured by the Epworth Sleepiness Scale (ESS), including assessment of episodes of sudden onset of sleep.
- 8. Modified Minnesota Impulse Disorders Interview (mMIDI).

3.0 STUDY DESIGN

3.1 Study Description

This is a Phase 3, international, multicenter, randomized, double-blind, placebo-controlled, parallel-group, 3-arm study with an open-label phase in levodopa-treated patients with PD experiencing end-of-dose "wearing-off". This study includes a Screening Period of up to 6 weeks that starts with a Screening Visit, a 24-week Double-Blind Treatment Period, a 52-week Open-Label Treatment Period, and a Safety Follow-Up Visit 4-weeks post-treatment. After providing written informed consent, patients will undergo screening evaluations. Patients must meet all inclusion criteria and none of the exclusion criteria, and they must successfully complete the diary training and achieve 80% overall diary concordance with the PD diary trainer/rater including at least 1 OFF interval to be considered for randomization. If preliminary eligibility is confirmed by the investigator and the Sponsor/Sponsor's designee, patients will then be scheduled for a Baseline Visit and will be required to return a valid set of Baseline diaries. Final eligibility will be determined at the Baseline Visit.

Eligible patients will be randomized in Part A to receive 1 of 2 tozadenant doses (60 mg BID or 120 mg BID) or placebo in a ratio of 1:1:1. Blinded IMP will be dispensed to patients at each study visit and will be taken BID (approximately 12 hours apart) for 24 consecutive weeks. Patients will return to the study site for evaluation at Weeks 2, 6, 12, 18, and 24. Patients will be contacted by telephone before the start of each 3-day PD diary completion period to be reminded to complete the diary for 3 consecutive days prior to their next scheduled visit. Patients will also be scheduled for a laboratory draw (hematology only) at Weeks 4, 8, 10, 16 and 22. Unscheduled Visits can be arranged as considered necessary by the investigator (see Section 6.2.34). In the event of Early Termination during Part A, patients will be asked to complete an Early Termination Visit as soon as possible (see Section 6.2.32) and then return 28 ± 3 days after their last dose of IMP for a Post-Early Termination Safety Follow-Up Visit (Section 6.2.35). Blinded safety data from the double-blind phase (Part A) will be provided to the Data and Safety Monitoring Board (DSMB), at a frequency specified by the DSMB charter, for ongoing monitoring of safety and detection of any trends. If requested by the DSMB, the DSMB statistician will provide unblinded safety data to the DSMB on a per needed basis, to enable a fully informed review.

During Part B, scheduled study visits for evaluations will take place at Weeks 26, 30, 36, 48, 60, and 76, and at Week 80 (Safety Follow-Up Visit). Patients will also be scheduled for a laboratory

draw (hematology only) at Weeks 28, 32, 34, 40, 44 and 68. The Safety Follow-Up Visit will occur 28 ± 3 days after the patient's last open-label dose of tozadenant. Patients who received tozadenant during Part A will continue on open-label tozadenant and those who received placebo will initiate open-label tozadenant. Neither the patient nor the investigator will be unblinded to the treatment received during Part A unless required for safety purposes as determined by the investigator and agreed to by the Sponsor. Upon starting Part B, patients will receive open-label tozadenant at a dose of 120 mg BID. Adjustments to the open-label tozadenant dose are allowed starting at Week 26 and at subsequent visits. Doses of 60 or 120 mg BID are permitted; the investigator may adjust a patient's dose to either level as clinically indicated. Because the information entered in the Interactive Response System (IXRS) will be used to manage the tozadenant inventory at each study site, timely entries into the IXRS will be important.

During Part B, patients' concomitant anti-PD medications may be adjusted as needed under the investigator's supervision (see **Section 5.9.1**). The optimal dose of open-label tozadenant for each patient will be defined following discussion between the patient and the investigator, taking into account the potential for improvement of disease symptoms and the tolerability profile.

During Part B, Unscheduled Visits can be arranged as considered necessary by the investigator (see Section 6.2.34). In the event of Early Termination during Part B, patients will be asked to complete an Early Termination Visit as soon as possible (see Section 6.2.33) and then return 28 ± 3 days after their last dose of IMP for a Post-Early Termination Safety Follow-Up Visit (Section 6.2.35). Safety data from Part B will be provided to the DSMB, at a frequency specified by its charter, for ongoing monitoring of safety and detection of any trends.

